LOCF2 (Up to Month 60)	Last post-baseline measurement in Follow-up period (2, 1849)	50

Adjustment for Multiplicity

The main objective of this Phase II trial is to select a dose regimen for further development in Phase III; therefore, no adjustment for multiplicity (except for dunnett adjustment for multiple comparisons used in the ANOVA models) resulting from multiple endpoints will be made. Caution should be used in interpreting significant p-values (p < 0.05). Interpretation of the results will involve global consideration of all efficacy results obtained in combination with an appropriate judgment of clinical relevance and consistency across endpoints.

Missing Data

As a general rule, all data collected and available will be used in the analysis. In general no imputation of missing data will be applied independently of the statistical method used to analyze the data, see however below remarks for LOCF in summaries over time.

The number of subjects contributing data will decrease over time. In summary assessments by time-point within DBPC, the LOCF method on post baseline observations will be used as sensitivity evaluation, and will be defined as LOCF1 for the 2-year analysis, and LOCF2 for the

analysis of the extended follow-up. These will only be included in summary tables (not in proc mixed models) and are considered exploratory and will be utilized for phase III statistical consideration. In the remainder of the SAP, if not otherwise stated, LOCF refers to both LOCF1 and LOCF2. Details for derivation of LOCF1 and LOCF2 for corresponding endpoints are provided in Table 3, 3a, and 3b.

Exceptions are handling of missing data from questionnaires where the guide for analysis prescribes otherwise, e.g. calculation depending on whether only single items are missing or a complete questionnaire is missing. If only single items are missing, the rules defined by the authors of the questionnaires (if any) will be followed.

The number and percentage of subjects with missing data for the primary and the secondary endpoints medial and lateral cartilage thickness, will be summarized by treatment group and timepoint for the mITT Analysis Set.

Listing of data

In general, all data will be listed by treatment group, subject and time point. Age, sex and race will be displayed in all listings.

ANOVA models

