ANOVA models are used for several endpoints. For each endpoint all available time-points except LOCF (specified in table 3) should be included and summarized. The general model specification for model that include 4 post-baseline measurements (i.e. qMRI) in SAS will be:

```
proc mixed data=p3 method=reml;
  class grpn vs usubjid CNTRGR1N ;
 model &var. = grpn vs grpn*vs base CNTRGR1N / solution;
  repeated vs / subject=usubjid type=&type. r;
  lsmeans grpn / adjust=dunnett diff=control('1') cl;
  lsmeans grpn*vs / adjust=dunnett diff=control('1' 'Week 26') cl;
  lsmeans grpn*vs / adjust=dunnett diff=control('1' 'Week 52') cl;
  lsmeans grpn*vs / adjust=dunnett diff=control('1' 'Week 78') cl;
 lsmeans grpn*vs / adjust=dunnett diff=control('1' 'Week 104') cl;
  lsmeans grpn*vs / slice=vs;
  contrast 'Linear trend (overall)' grpn -2 -1 0 1 2;
  contrast 'Linear trend at Week 26' grpn -2 -1 0 1 2 grpn*vs -2 0 0 0 -1 0 0
0 0 0 0 0 1 0 0 0 2 0 0 0;
  contrast 'Linear trend at Week 52' grpn -2 -1 0 1 2 grpn*vs 0 -2 0 0 0 -1 0
0 0 0 0 0 0 1 0 0 0 2 0 0;
  contrast 'Linear trend at Week 78' grpn -2 -1 0 1 2 grpn*vs 0 0 -2 0 0 0 -1
0 0 0 0 0 0 0 1 0 0 0 2 0;
  contrast 'Linear trend at Week 104' grpn -2 -1 0 1 2 grpn*vs 0 0 0 -2 0 0 0
-1 0 0 0 0 0 0 0 1 0 0 0 2;
```

run;

12 Disposition of Subjects and Discontinuations

This section presents specifications for reporting subject disposition and treatment/trial discontinuations. Additionally, procedures for reporting protocol deviations are provided.

Subject disposition will be presented for all subjects and by treatment group in terms of:

- Total number of subjects screened (i.e. subjects who signed informed consent)
- Number and percentages of subjects discontinuing the trial prior to randomization divided by main reason for discontinuation (did not meet all eligibility criteria, withdrew consent, other), by country and site, and overall.
- Number and percentages of randomized subjects.
- Number and percentages of exposed subjects
- Number and percentages of randomized subjects who completed the DBPC treatment phase. For the 2-year analysis a completer is a subject with no date of study discontinuation before day 819.
- Number and percentages of randomized subjects who discontinued the trial after randomization, during DPBC i.e. before day 819, and during extended follow up phase (grouped by treatment) and main reason (AE, death, lost to follow-up, etc).

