The treatment effect on the primary endpoint will be assessed through dose-ranging using a repeated measurement analysis of variance (ANOVA) (using PROC MIXED in SAS) on absolute change from baseline, including the treatment group, the time point, and the (pooled) country as fixed factors and the baseline value as covariate and treatment by time point as interaction, see "ANOVA models" in section 11. Repeated measures over time will be accounted for using an 'unstructured' covariance pattern, and if the model fails to converge 'compound symmetry' will be used.

If the null hypothesis is rejected, the alternative hypothesis will be accepted and it will be concluded that there is a dose relationship versus placebo over time.

The analysis of the primary efficacy endpoint will also consist of testing the overall treatment effect at 2 years and will therefore only be conducted for the DBPC treatment phase.

The significance level will be set at 5% two-sided.

For the overall treatment effect testing, the null and alternative hypotheses will be:

```
H0: Mean (Placebo) = Mean (180 mcg) = Mean (360 mcg) = Mean (600 mcg) = Mean (1200 mcg) H1: Mean (i) \neq Mean (j) for some i \neq j and i, j = Placebo or 180 mcg or 360 mcg or 600 mcg or 1200 mcg.
```

where the doses shown are the total doses of sprifermin to be administered over the DBPC treatment phase.

If the null hypothesis is rejected, the alternative hypothesis will be accepted and it will be concluded that there is at least one group that differs from the other groups.

Pairwise comparisons of absolute change from baseline in cartilage thickness (sprifermin treatment groups versus placebo) will be performed within the context of this modeling framework. For each pairwise comparison, the difference between treatments and the corresponding 95% CI and p-value will be presented. P-values (corresponding to Type 3 tests of fixed effects) will be reported for all covariates in the original 'Overall' model for all time points combined (i.e. baseline value, treatment, timepoint, treatment-by-timepoint interaction, country) and for all timepoints. Estimated coefficients, p-values and 95% CIs will be presented overall and at each timepoint for

(i) the dose relationship (linear trend); and, (ii) each pairwise comparison between dose level and placebo.

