16.2 Secondary Efficacy Endpoint Analyses

Secondary endpoints related to structure:

Cartilage thickness

Cartilage thickness in the medial and lateral compartments will be summarised per timepoint (including LOCF) along with absolute and relative change from baseline. These will be calculated in two ways corresponding to the calculation of cartilage Average and Total thickness:

- 1. Medial
 - a. MFTC.VC/(cMF.tAB+MT.tAB), primary
 - b. MFTC ThCtAB aMe
- 2. Lateral:
 - a. LFTC.VC/(cLF.tAB+LT.tAB), primary
 - b. LFTC ThCtAB aMe

All these variables will be included in the ADAM. Only (1a) and (2a) will be used in summaries and analyses, the others (1b) and (2b) will only be derived in ADaM.

The absolute change from baseline in the medial and lateral compartments over 2 years will be analysed using a similar ANOVA model as the model used for the primary endpoint. Similarly to the analysis of the primary end-point, sensitivity analyses on ranked data will also be performed.

Cartilage Volume

Cartilage volume in the medial and lateral compartments as well as in the total femorotibial joint will be summarised per timepoint (including LOCF) along with absolute and relative change from baseline. These will be calculated as MFTC.VC, LFTC.VC, and MFTC.VC + LFTC.VC respectively.

The absolute change from baseline over 2 years will be analysed using a similar ANOVA model as the model used for the primary endpoint.

Joint Space Width

Minimal JSW (mJSW) in the medial and lateral compartments will be summarised per timepoint (including LOCF) as well as absolute and relative change from baseline for target knee as well as for contralateral knee.

The absolute change from baseline over 2 years will be analysed using an ANOVA model similar to the primary endpoint for target knee only.

Secondary endpoints related to function and symptoms:

WOMAC Total Score

WOMAC total scores (and WOMAC sub scores, as described below) will be displayed descriptively after being transformed to a scale of 0 to 100 using the formula described below.

All items have 11 possible answers ranging from 0 (no problems) to 10 (extreme problems). Given items I1 to Ix as the answers to each questionnaire item on a given subscale and the raw score as the *arithmetic mean* of the respective non-missing answers of items I1 to Ix, the subscale summary score will be calculated as:

$$\left[\frac{(mean\ score\ of\ subscale)}{10}\right]\cdot 100$$

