The WOMAC total score, and absolute changes from baseline in the WOMAC total score for the target knee will be presented with summary statistics for all timepoints (including baseline, post-treatment, and LOCF).

Absolute change from baseline in WOMAC total score over 2 years will be considered a continuous variable and will be analysed using a model similar to the ANOVA model used for the primary endpoint.

If an entire questionnaire is missing for a time point, no imputations will be performed for that time point. If some items are missing, imputation for Total score (and for sub scores) will be performed using same principal used for KOOS.

WOMAC Sub Scores

WOMAC sub scores (weight-bearing pain score (sum of items: walking, going up and down stairs, and standing), pain, function and stiffness) will be tabulated descriptively as described above for Total score.

Absolute change from baseline in pain, function, stiffness, and weight-bearing pain, over 2 years will be analysed using a model similar to the ANOVA model described under primary endpoint.

WALK test

Time needed to complete the 20-meter walk tests as well as absolute change from baseline will be presented with summary statistics per timepoint (including LOCF). No imputation for missing data will be done. Absolute change from baseline in time needed to complete the 20-meter walk will be analysed using a model similar to the ANOVA model described under primary endpoint.

Patient Global Assessment (PGA)

The Patient Global Assessment is based on subject's answer to the question "Considering all the ways your osteoarthritis of the knee has affected you during the last 48 Hours, select the number that best describes the impact of your knee osteoarthritis on your daily life", and can take on values between 0-10 (0=None, 10=Extreme), for summaries the values are rescaled to 0-100 by multiplication with 10.

The Patient Global Assessment will be presented with summary statistics per timepoint (including LOCF) as well as absolute change from baseline. Mean score will be presented as described for continuous variables, and also number and percentages per score will be presented. No imputation for missing data will be done (except LOCF).

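### Each per-visit Dunnett statement in the SAP adjusts over 19 group-by-visit differences, although only four sprifermin-versus-placebo comparisons are planned at each visit

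*SAP*

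**What the plan says.** The code is in SAP Section 11 under the heading ANOVA models. It is introduced with "The general model specification for model that include 4 post-baseline measurements (i.e. qMRI) in SAS will be". The fixed effects are treatment group (`grpn`, 5 levels), visit (`vs`, Weeks 26, 52, 78 and 104), their interaction, the baseline value and pooled country.

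Two kinds of Dunnett statement follow.
- One for treatment averaged over visits: "lsmeans grpn / adjust=dunnett diff=control('1') cl".
- Four for the interaction, one per visit. The last is "lsmeans grpn*vs / adjust=dunnett diff=control('1' 'Week 104') cl".

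SAP Section 16.1 says which comparisons are wanted: "Estimated coefficients, p-values and 95% CIs will be presented overall and at each timepoint for" the linear trend and "ii) each pairwise comparison between dose level and placebo". That makes four comparisons at each visit.

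The multiplicity paragraph of SAP Section 11 gives the rule as "no adjustment for multiplicity (except for dunnett adjustment for multiple comparisons used in the ANOVA models". It does not say which comparisons form the Dunnett family. Protocol Section 8.5.1 plans no multiplicity adjustment at all.

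**The concern.** In the interaction statements the control is a single cell, placebo at the named visit, and every other cell of the interaction is compared with it. The Week 104 statement therefore also contains differences such as 1200 mcg at Week 26 against placebo at Week 104, or placebo at Week 52 against placebo at Week 104. These mix treatment with time and are not planned anywhere, yet they raise the Dunnett critical value that is applied to the four planned differences.

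The trend contrast and the overall test do not show which regimens differ from placebo. The per-visit pairwise comparisons do, and SAP Section 11 gives selection of a dose regimen as the main objective of the trial. If the adjusted values are the ones tabulated, a regimen could pass a four-comparison Dunnett test at Week 104 and still be shown with an adjusted p-value well above 0.05.

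**Working it through.** **Inputs.** From the documents: 5 groups in equal allocation, 4 post-baseline MRI visits, SD 0.10 mm, 76 evaluable subjects per group, and assumed 2-year changes of -0.03, -0.01, +0.01, +0.01 and +0.03 mm (SAP Section 7). Not in the documents, and therefore assumed and varied: within-subject correlation, pattern of SD over visits, and numbers per visit. Degrees of freedom are taken as 5 × (76 - 1) = 375.

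**The plan's own figures.** The documents state no Dunnett critical value. Their design figures do reproduce: overall F-test power at 76 per group is 90.4% (stated 90%), and 76/0.70 = 108.6, rounded up to 109 per group, or 545 in total.

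**Size of the family.** Interaction cells: 5 × 4 = 20. Differences from one control cell: 20 - 1 = 19, made up of:
- 4 sprifermin cells at the same visit (planned);
- 4 × 3 = 12 sprifermin cells at other visits (not planned);
- 3 placebo cells at other visits (not planned).

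**Critical values.** These are the simulated 95% quantile of max|t| over the family. Correlation ranged over 0 to 0.9, with compound-symmetric and serial patterns. SD was constant or rising over visits, and numbers were equal or falling over visits.

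| Family | Critical abs(t) |
|---|---|
| One comparison, unadjusted | 1.97 |
| Four same-visit comparisons | 2.45 |
| 19 as coded, Week 104, constant SD | about 2.78 to 2.91 |
| 19 as coded, Week 104, SD rising, with or without falling numbers | about 2.73 to 2.80 |
| 19 as coded, Week 26, SD rising, with or without falling numbers | about 2.9 to 2.97 |

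**Width at Week 104.** SE = 0.10 × √(2/76) = 0.0162 mm.
- Four comparisons: 2.45 × 0.0162 = 0.040 mm.
- As coded: 2.73 × 0.0162 = 0.044 mm to 2.91 × 0.0162 = 0.047 mm.
- Ratio: 2.73/2.45 = 1.11 to 2.91/2.45 = 1.19.

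**Error rate and p-values.** The chance under the null that any of the four planned differences exceeds the 19-cell critical value is about 1.2 to 2.4%, instead of 5%. A result whose four-comparison adjusted p is 0.05 comes out at about 0.10 to 0.19. Both ranges cover the visits examined, Weeks 26 and 104.

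**Illustrative power at Week 104.** Noncentral t, noncentrality = difference/SE, 375 df, 76 per group. The differences are those the SAP assumes against placebo: 0.03 - (-0.03) = 0.06 mm for 1200 mcg, and 0.01 - (-0.03) = 0.04 mm for 360 and 600 mcg.

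| Difference | Unadjusted | Family of four | As coded (2.73 to 2.91) |
|---|---|---|---|
| 0.06 mm | 96% | 89% | 78 to 83% |
| 0.04 mm | 69% | 51% | 33 to 40% |

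The power figures ignore the baseline covariate and the information from earlier visits. Nothing was run in SAS.

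**The case against.** **The family of four is not stated.** The SAP nowhere promises 5% familywise error within a visit; its 5% two-sided level belongs to the trend and overall tests. Pairwise comparisons at each of four visits could be read as a family of 4 × 4 = 16. With constant SD and complete data, 16 same-visit comparisons have a critical value of 2.76 to 2.93, and the coded threshold gives about 4.5 to 5.5% error over them. This stands to the extent that the phrase too conservative has meaning only relative to a per-visit family of four. It does not rescue the code. No statement contains those 16 differences, each contains 15 unplanned ones, and the similar critical value is a coincidence.

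**Reported results may not change.** The `cl` statements also give unadjusted values. The SAP does not say which set is tabulated, and the table shells, which could settle it, are a separate document. This stands. But tabulating the adjusted values brings in the unplanned differences, while tabulating the unadjusted ones leaves the Dunnett exception in Section 11 without effect on the reported comparisons.

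**No decision hangs on the adjusted p-value.** This also stands. SAP Section 11 asks for global consideration of all efficacy results. A reader might infer that an effective regimen would be dropped because of this code, but the documents contain no such gate. The SAP also says that its power calculations made no multiplicity adjustment, so the power figures above breach no planned power.

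**Other endpoints.** A reader might infer the same fault for joint space width, where the SAP says "The absolute change from baseline over 2 years will be analysed using an ANOVA model similar to the primary endpoint for target knee only", and for WOMAC total score, which "will be considered a continuous variable and will be analysed using a model similar to the ANOVA model used for the primary endpoint". No code is printed for those models, so the point is established only for the four-visit MRI model.

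**Conclusion.** The mismatch is real: 19 differences are adjusted for in each per-visit statement and four are planned. That count follows from the code and needs no assumption. The conservative direction held in every setting tried. The size, measured against a per-visit family of four, rests on the assumed correlation, variance pattern and numbers per visit. The wide ranges are the right ones to quote, because Section 16.1 specifies an unstructured covariance and the mITT set admits subjects with a single post-treatment MRI, so constant SD and equal numbers over visits cannot be taken for granted.

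A reader might go further and infer that the primary analysis is compromised. It is not. The linear-trend contrasts and the slice test use no Dunnett adjustment, the `lsmeans grpn` statement already has exactly four differences, and point estimates and unadjusted limits do not depend on the family. What is affected is the set of adjusted per-visit p-values and confidence limits. The matter should be corrected before unblinding, but it does not threaten the primary conclusions.

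**What to change.** In SAP Section 11, define the Dunnett family in words and make the code match.

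- **Per-visit family:** restrict each adjustment to the four same-visit sprifermin-versus-placebo differences, for example with a per-visit `SLICE` of `grpn*vs` using Dunnett differences against placebo, or with `LSMESTIMATE` and a four-comparison adjustment.
- **Family across visits, if that is intended:** say so, and code only the 16 same-visit differences.
- **Reporting:** state whether the tabulated pairwise p-values and limits are adjusted or unadjusted, and align the table shells.
- **Other models:** use the same restricted form in any other repeated-measures model that reuses this code.

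The cost is a few lines of code and two or three sentences of text. No data, sample size or primary test changes.

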16.1 Primary Efficacy Endpoint Analyses

The primary endpoint for the DBPC treatment phase is the change from baseline in cartilage thickness in the total femorotibial joint as evaluated by quantitative MRI at 2 years in the mITT. Cartilage thickness of the total femorotibial joint will be calculated in two ways:

- 1. Average Cartilage Thickness (Total Volume divided by Total Surface Area): (MFTC.VC+LFTC.VC)/(cMF.tAB+cLF.tAB+MT.tAB+LT.tAB)
- 2. Total Cartilage Thickness (sum of cartilage thickness in medial and lateral compartment): MFTC_ThCtAB_aMe + LFTC_ThCtAB_aMe

These 2 variables are highly correlated, but since the first one (average) was used in the previous study as primary endpoint and power was based on this variable, this will be also the variable to be used as primary endpoint. Of these two (1) is considered the primary, and only this is summarized and analyzed, (2) is just derived in ADaM. Definitions of these variables are provided in the imaging transfer specifications document.

Summary statistics

Summary statistics for change from baseline in cartilage thickness in the total femorotibial joint will be presented both for the DBPC treatment phase and for the follow-up phase.

Summary statistics will be provided per timepoint (including LOCF) for:

- Cartilage thickness in the femorotibial joint as evaluated by quantitative MRI
- absolute change from baseline in cartilage thickness by quantitative MRI
- percentage change from baseline in cartilage thickness by quantitative MRI

Primary analyses of linear dose-relationship and treatment effect

The primary efficacy analyses will consist of testing the linear dose relationship at 2 years and the treatment effect and will be presented for the DBPC treatment phase.

Sprifermin (AS902330) Statistical Analysis Plan (Final) EMR700692 006 – v1.0

The significance level will be set at 5% two-sided.

For the linear dose relationship testing, the null and alternative hypotheses will be conducted using the following linear contrast testing:

```
H0: -2 Mean (Placebo) - 1 Mean (180 mcg) + 0 Mean (360 mcg) + 1 Mean (600 mcg) + 2 Mean (1200 mcg) = 0 H1: -2 Mean (Placebo) - 1 Mean (180 mcg) + 0 Mean (360 mcg) + 1 Mean (600 mcg) + 2 Mean (1200 mcg) \neq 0
```

where the doses shown are the total doses of sprifermin to be administered over the DBPC treatment phase.

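### The printed mixed-model code adjusts each per-visit Dunnett set over 19 differences instead of 4, and its 2-year trend contrast depends on a visit order that is not stated

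*SAP*

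**What the plan says.** SAP Section 11 (ANOVA models) gives SAS code as the general specification for endpoints with four post-baseline visits. It opens with "proc mixed data=p3 method=reml" and "class grpn vs usubjid CNTRGR1N", where `grpn` is treatment and `vs` is visit. The procedure line carries no option that sets the order of the class levels.

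The dose comparisons at 2 years come from "lsmeans grpn*vs / adjust=dunnett diff=control('1' 'Week 104') cl", with matching lines for Weeks 26, 52 and 78. The 2-year trend comes from a contrast that begins "contrast 'Linear trend at Week 104' grpn -2 -1 0 1 2 grpn*vs 0 0 0 -2 0 0 0" and continues to 20 interaction coefficients.

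On multiplicity, Section 11 makes no adjustment "except for dunnett adjustment for multiple comparisons used in the ANOVA models". It does not define the family.

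Section 16.1 says what is wanted: "The primary efficacy analyses will consist of testing the linear dose relationship at 2 years and the treatment effect". It adds: "Estimated coefficients, p-values and 95% CIs will be presented overall and at each timepoint for" (i) the linear trend and (ii) "each pairwise comparison between dose level and placebo".

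**The concern.** Three things in the code do not match the text it is meant to implement.

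- **Dunnett family.** The per-visit lines act on the treatment-by-visit interaction, so the adjustment covers comparisons across visits that no objective asks for. Dunnett is the plan's only multiplicity adjustment, and the stated aim is to choose a dose regimen. Adjusted per-visit p-values and intervals that are too strict therefore bear on the trial's main use.
- **Visit order.** The trend coefficients are assigned by position, and nothing printed fixes which visit stands in which position. The trend at 2 years is a primary test. If the order were wrong, its p-value would come from the Week 78 scan, which the Table 3 footnote takes before that visit's injection, hence before cycle 4. The contrast label would not show this.
- **Trend estimate.** Section 16.1 requires estimated coefficients and 95% CIs for the trend. The printed CONTRAST statements return tests only.

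**Working it through.** **1. Inputs, and the plan's own figures.** From SAP Section 7: mean changes of -0.03, -0.01, +0.01, +0.01 and +0.03 mm (placebo, 180, 360, 600, 1200 mcg), SD 0.10 mm, two-sided 5%.

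- Trend = -2(-0.03) - 1(-0.01) + 0(0.01) + 1(0.01) + 2(0.03) = 0.14 mm. At 55 per arm, SE = 0.10 x sqrt(10/55) = 0.0426 and the noncentral-t power is 0.905 (plan: 90%).
- Overall F test at 76 per arm: power 0.904 (plan: 90%).
- 76/0.7 rounds up to 109 per arm, and 5 x 109 = 545.

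The design figures reproduce and are not in question.

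**2. Size of the Dunnett family.** There are 5 arms x 4 visits = 20 cells, one of which is the control, so each line gives 19 differences. For the Week 104 line:

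- 4 compare a dose with placebo at Week 104 (wanted);
- 3 compare placebo at another visit with placebo at Week 104;
- 12 compare a dose at another visit with placebo at Week 104.

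So 15 of 19 are not asked for. Over four lines that is 60 of 76.

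**3. Effect on the adjustment.** The within-subject correlation is not in the documents, so a range is shown. Critical values are simulated (1,000,000 draws, 375 df, 76 complete subjects per arm, equal variances). Half-width = critical value x 0.10 x sqrt(2/76). Over 4 differences the critical value is 2.45 and the half-width 0.040 mm. Over 19:

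| Assumed correlation | Critical value | Interval width ratio | Half-width (mm) |
|---|---|---|---|
| 0.3 | 2.90 | 1.18 | 0.047 |
| 0.5 | 2.88 | 1.18 | 0.047 |
| 0.7 | 2.85 | 1.16 | 0.046 |
| 0.9 | 2.78 | 1.13 | 0.045 |

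A separate simulation on the normal scale (400,000 draws) gave 2.77 to 2.88 against 2.44 to 2.45. In it, the chance under the null that any of the 4 wanted comparisons exceeds the 19-difference threshold was 1.4% (correlation 0.3) to 2.1% (0.9). A result with a 4-comparison adjusted p of 0.05 would print as 0.15 to 0.12.

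Pairwise power at 76 per arm for the planned differences from placebo:

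| Difference | Unadjusted | Over 4 | Over 19 (correlation 0.3 to 0.9) |
|---|---|---|---|
| 0.04 mm (360 or 600 mcg) | 0.69 | 0.51 | 0.33 to 0.38 |
| 0.06 mm (1200 mcg) | 0.96 | 0.89 | 0.79 to 0.82 |

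**4. Which visit each trend contrast tests.** Each 20-coefficient row, laid out as 5 arms x 4 visits, has one non-zero column (-2, -1, 0, 1, 2). A text sort of the unpadded labels gives Week 104, Week 26, Week 52, Week 78.

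| Printed label | Column | Chronological order | Text order |
|---|---|---|---|
| Week 26 | 1 | Week 26 | Week 104 |
| Week 52 | 2 | Week 52 | Week 26 |
| Week 78 | 3 | Week 78 | Week 52 |
| Week 104 | 4 | Week 104 | Week 78 |

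An extra blank before 26, 52 and 78 would restore chronological order. Treatment coding is not in doubt: the logistic code in Section 16.5 shows that `grpn` runs from placebo to 100 mcg x4 in dose order.

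**5. Possible power effect of a misordering.** No Week 78 means are given, so this is illustration only. At 76 per arm, SE = 0.10 x sqrt(10/76) = 0.0363. If 100%, 75% or 50% of the 0.14 mm contrast were present at Week 78 with the same SD, the noncentrality would be 3.86, 2.89 or 1.93 and the power 97%, 82% or 49%, against 97% intended at Week 104.

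**The case against.** The case for treating this as a small clarification has real substance.

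- The code is a template with macro placeholders and an undefined input dataset. How `vs` is built is not shown, and padding in the labels may have been lost when the text was extracted. The default sort rule is software behaviour, not something the documents state. All of this stands, so the visit-order point is conditional.
- Section 16.1 states the 2-year trend hypothesis in words and symbols, and outputs are to be produced in a validated environment. The class-level and solution output would reveal the level order, and the Week 104 LS-means and slice test are labelled by level. That makes a mislabel discoverable, but it does not put the order into the plan.
- No sentence sets the Dunnett family at 4, Section 16.1 does not say that its intervals are adjusted, the CL option also prints unadjusted limits, and the table shells are separate documents. So it is unknown which numbers will be reported. However, Section 16.1 asks for each dose against placebo at each visit, and the SAP's own overall line on `grpn` adjusts over exactly 4. Nothing supports 19.
- The Dunnett error is conservative and touches neither primary test. That is correct and limits its weight.

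**Conclusion.** The point holds, with parts of different certainty.

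- **Certain, given that the adjustment covers every difference a line produces:** each per-visit Dunnett line uses 19 differences where Section 16.1 needs 4. Adjusted intervals are 13% to 18% wider than necessary for correlations of 0.9 down to 0.3. Estimates, unadjusted pairwise p-values, the trend contrasts, the slice test and the sample size are not affected.
- **Certain:** the trend contrasts are positional and the visit order is not stated.
- **Conditional on unpadded labels sorted as text:** all four visit-specific trend p-values carry the wrong label, including the one used for a primary test. The overall trend, the Week 104 slice test, the LS-means and the unadjusted pairwise results would still be right. No delivered result is shown to be wrong.
- **Certain but minor:** the code does not produce the trend estimates and intervals that Section 16.1 promises.

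This should be fixed before lock. A primary p-value should not rest on an unstated sort order, and the plan's one multiplicity adjustment should match its stated comparisons.

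**What to change.** Before database lock and unblinding:

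1. Use the numeric MRI visit codes of SAP Table 3 (3, 5, 7, 9 for Weeks 26, 52, 78, 104) as `vs`, unformatted or with ORDER=INTERNAL, and adapt the control levels to match.
2. Print the contrast coefficient matrix on blinded data and confirm that each row picks the visit in its label.
3. Replace the four interaction Dunnett lines with per-visit sets of 4 comparisons with placebo.
4. State which pairwise p-value and interval (adjusted or unadjusted) will be reported.
5. Add ESTIMATE statements, or an equivalent, with 95% CIs for the trend overall and at each visit.
6. Apply the same checks to the other endpoint models in Section 16.2. Questionnaire endpoints have 8 post-baseline visits to Week 104 in Table 3, so the same pattern there would give 5 x 8 - 1 = 39 differences per line.

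The cost is a few lines of SAP code and one check on blinded data. No operational step, sample-size figure or power statement changes.
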